5.4.7 Pulmonary Assessment

Pulmonary assessments will be made at screening, end of study and Weeks 12, 24, 36 and 48 during the first 48 weeks and then 6 monthly during the extension phase. If a subject withdraws from the study prematurely they will also be assessed at the termination visit.

The predicted spirometry assessments will be adjusted for age and sex. Assessments will be adjusted for race as shown in the [Table 1](#) of section 6.4.5 in the protocol. These adjustments are made at the site by the spirometry software.

FEV₁, FVC, MIP, MEP and PEF will be measured. Changes from baseline will be calculated.

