	Entry Phase/ Baseline Phase	Treatment Phase Cohorts 1, 2 and 3 To be repeated at the time points below in each year of the treatment phase until either SMT C1100 is approved in the relevant countries or development of SMT C1100 is discontinued.				Early termination visit	Approval/ Discontinuation
	W48 of original Phase Out DMD ^h	12 W +/- 2 w ^g	24 W +/- 2 w	36 W +/- 2 w ^g	48 W +/- 2 w		Approval +/- 2 w
Informed consent and assent	X						
Vital signs	X	X	X	X	X	X	X
Physical examination	X		X		X	X	X
12-lead electrocardiogram	X ^a		X ^b		X ^b	X ^b	X ^b
Echocardiogram	X		X ⁱ		X ⁱ	X	X
Pulmonary assessments ^c	X		X		X	X	X
Haematology, clinical chemistry, coagulation parameters ^f , and urinalysis	X	X	X	X	X	X	X
Liver function tests, including glutamate, dehydrogenase, amylase, and lipase	X	X	X	X	X	X	X
Leg MRI (Cohort 1 and 2 only)	X		X		X	X	
Cardiac MRI (Cohort 3 only)	X				X	X	
NSAA	X		X		X	X	X
10 metre run/walk,	X		X		X	X	X
Six minute walk distance/test	X		X		X	X	X
PODCI, EQ-5D,UL- PROM,	X		X		X	X	X
PUL	X		X		X	X	X
Blood biomarkers ^d .	X		X		X	X	X
SMT C1100 parent and metabolites PK	X		X ^e		X ^e	X	X
SMT C1100 bid dosing	X	X	X	X	X		
Adverse event recording	X	X	X	X	X	X	X
Concomitant medications	X	X	X	X	X	X	X

Study Number: SMT C11005	Compound No.: SMT C1100
Protocol	Version: 5.0 24Feb2017

If multiple assessments are at the same time point, it is appreciated that some deviation in timing will be necessary. A \pm 15 minute window is acceptable with pharmacokinetic samples being performed as close to scheduled time point as possible. Please see the study manual for more information on timing.

- a. ECG at 0.5,2,4 and 6 h after am dose
- b. ECG at a single time point 4 hours after dosing
- c. Pulmonary assessments include forced expiratory volume in 1 second, peak expiratory flow, forced vital capacity, maximum inspiratory pressure and maximum expiratory pressure
- d. Plasma biomarkers include creatine kinase, matrix metalloproteinase 9, and others, as well as quantification of changes of proteins. Note: creatine kinase and MMP-9 will not be collected at Week 1.
- e. Each patient will have single PK samples taken at 4 h post-AM dose
- f. Coagulation parameters for Cohort 2 and Cohort 3 only.

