4.2 Secondary Endpoints

- Change from baseline to Week 24 or 48 in utrophin expression via muscle biopsy analysis (Cohorts 1 and 2)
- Change from baseline to Week 24 or 48 in muscle regeneration biomarkers via muscle biopsy analysis (Cohorts 1 and 2)
- Change from baseline to Weeks 12, 24, 36 and 48 (Cohorts 1 and 2) and from baseline to Weeks 1, 24 and 48 (Cohort 3) in pulmonary function tests
- Safety data including:
 - Vital signs (systolic and diastolic blood pressure and heart rate)
 - Physical examination
 - Twelve-lead electrocardiogram (ECG)
 - Echocardiogram (ECHO)
 - Pulmonary function tests:
 - Forced expiratory volume in 1 second (FEV₁)
 - Forced vital capacity (FVC)
 - Maximum inspiratory pressure (MIP)
 - Maximum expiratory pressure (MEP)
 - Peak expiratory flow (PEF)
 - Peak cough flow (PCF) (Cohort 3)
 - Sniff nasal inspiratory pressure (SNIP) (Cohort 3)
 - Safety laboratory evaluations (clinical chemistry, haematology, (all 3 Cohorts) coagulation (Cohort 2 and Cohort 3) parameters and urinalysis (all 3 Cohorts))

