5.2 Efficacy Assessments

All of the efficacy endpoints will be assessed at baseline, end of study, and Weeks 12, 24, 36 and 48 during the first 48 weeks and then 6 monthly during the extension phase. If a subject withdraws from the study prematurely they will also be assessed at the termination visit.

The 6MWT will also be conducted at screening.

In the sections below reference is made to reasons for not performing an assessment or not completing an assessment. Different approaches will be taken for dealing with the missing data dependent on whether or not the reason is related to the subject's medical condition (i.e. informative). A reason of 'Subject physically unable' will be regarded as informative, whilst 'Site staff/facility unavailable' is not informative. Other reasons will require a team review on a case-by-case basis.

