9.0 Statistical Methods

9.1 General

All statistical analyses will be performed using SAS (Version 9.4).

Unless otherwise specified, descriptive data summaries will be tabulated for all endpoints. Categorical data will be summarized using number of subjects (n), frequency and percentages of subjects falling into each category, with the denominator for percentages being the number of subjects in the study population, unless otherwise noted. Percentages will be rounded to one decimal place except for 100%, which will have no decimal place. Counts of zero will not display a percentage.

All continuous variables will be summarized using mean, standard deviation, median, Q1, Q3, minimum, maximum, and number of subjects with observations. The mean, median will be presented to one decimal place greater than the original data, standard deviation will be to two decimal places greater than the original data, and the minimum and maximum will have the same number of decimal places as the original data.

For both categorical and continuous variables the number of missing values will be presented in summary tables and will be split by the number of missing values due to discontinuation of treatment and due to missing. Subjects will only be counted if they had the potential to reach the visit (e.g. a subject who has been in the study 48 weeks will not be considered as having a missing Week 60 visit). Their potential to reach a visit is based on the duration of time they could have been in the study, from their first dosing date till the datacut date. If a subject does not have a record for a visit and did not discontinue treatment, then the record will be counted as due to missing. For subjects who discontinue treatment then the date of discontinuation will be considered as the date of the last dose of study medication plus 1 day, any missing records prior to this date will be classed as missing and any missing records after this date will be

classed as discontinued. The target study day for a visit will be used to assess whether a subject could have had a visit prior to discontinuation of treatment.

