9.7.3 Fibre Regeneration (via Biopsy) (Cohorts 1 and 2)

All analyses will be performed on the Biopsy population.

Tabulations will be over all subjects and will not provide separate information for the different cohorts.

Imputation will not be used for missing data with summaries and plots, and so subjects with missing baseline or Week 24/48 data will be excluded from presentations for the relevant time-point and change from baseline presentations. However, mixed effect models will be used to make comparisons to baseline; these analyses will use all available data and adjusts the results for missing data under the assumption of missing at random.

Summary tables will acknowledge the number of subjects who have their biopsy performed at Week 24 and Week 48 (e.g. if a subject isn't supposed to have a Week 24 measurement it will not be counted as missing).

The total number of fibres assessed with each assay will be summarized using descriptive statistics (n, median, Q1, Q3, minimum and maximum) by visit. These variables won't be included in any other analyses.

The percentage of fibres (%fibre) with 0, 1, 2 and 3 MHCd/Utrphin intensity will be excluded from analyses unless specifically mentioned.

For each assay (Myosin and Utrophin) the number of subjects contributing 1 or 2 samples worth of data will be tabulated for each visit for each of the two groups (Week 24 and Week 48). Where there is 1 sample with data the number of subjects with 1, 2 and 3 sections will be tabulated and where there are 2 samples with data the number of subjects with 2, 3, 4, 5 and 6 sections will be tabulated.

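### SAP 5.4.7 and 5.2 give Cohort 3 the Cohort 1–2 visit schedule and omit PCF and SNIP, so SAP 9.1 counts never-scheduled tests as missing and the all-subjects lung-function column changes mix by visit

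*SAP*

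**What the plan says.** **Lung function, assessment definition.** SAP 5.4.7 makes no cohort split: "Pulmonary assessments will be made at screening, end of study and Weeks 12, 24, 36 and 48 during the first 48 weeks". After FEV1, its parameter list reads "FVC, MIP, MEP and PEF will be measured. Changes from baseline will be calculated". Week 1, PCF and SNIP do not appear.

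**Lung function, endpoint list.** For Cohort 3, SAP 4.2 specifies change "from baseline to Weeks 1, 24 and 48 (Cohort 3) in pulmonary function tests". It names PCF for Cohort 3 and also "Sniff nasal inspiratory pressure (SNIP) (Cohort 3". Protocol 3.2 and 6.4.5 agree. The protocol's Cohort 3 Time and Events table marks pulmonary tests at screening, Day 1, Day 7, Weeks 24 and 48, early termination and end of study. Weeks 4, 12 and 36 are blank, and footnote a lists seven parameters.

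**Functional tests.** SAP 5.2 says, with no exception for Cohort 3: "All of the efficacy endpoints will be assessed at baseline, end of study, and Weeks 12, 24, 36 and 48". The Cohort 3 table schedules these tests at screening and Weeks 24 and 48 (plus early termination and end of study). SAP 4.3 gives Cohort 3 only Weeks 24 and 48 for 6MWD, NSAA, PODCI and PUL, but does not split the timed function tests.

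**Counting and pooling.** SAP 9.1 sets the rule for any boy who "does not have a record for a visit and did not discontinue treatment, then the record will be counted as due to missing". Whether a boy could have reached a visit depends on elapsed time since first dose, not on whether the test was planned. A not-scheduled exemption is stated only for biopsies, in SAP 9.7.3: a subject not "supposed to have a Week 24 measurement it will not be counted as missing". By default, SAP 9.1 tabulates each cohort and all subjects together. SAP 10.0 bars pooling of Cohort 3 with Cohorts 1 and 2 for efficacy data, whereas the SAP handles lung function under safety (5.4.7, 9.8.8).

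**Extension.** Footnote c of the protocol's extension table reads "Pulmonary assessments include forced expiratory volume in 1 second, peak expiratory flow, forced vital capacity, maximum inspiratory pressure and maximum expiratory pressure", without PCF or SNIP.

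**The concern.** Protocol 1.2 explains that Cohort 3 was added to give cardiac and respiratory data in boys likely to be at risk of cardio-respiratory decline. Its respiratory measures should therefore have a clear analysis definition. Section 5.4.7 looks like the Cohort 1–2 text carried over: the SAP's laboratory, ECG and PK sections are all split by cohort, and its echocardiogram section is limited to Cohorts 1 and 2.

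Three things are at stake:

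- Two of Cohort 3's seven pulmonary measures have no assessment definition, and no analysis section names them.
- Completeness tables would report losses of data that were never due.
- An all-subjects lung-function trend would move partly because Cohort 3 enters at some visits and leaves at others.

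**Working it through.** **Inputs**

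- Planned sizes (SAP 3.1): 30 in Cohort 1, about 10 in Cohort 2, about 15 in Cohort 3.
- Pulmonary schedules: the protocol's Time and Events tables.
- Visit windows (SAP 5.1): Week 12 is days 67–112; Week 36 is days 224–280.
- Assumption: full enrolment and no dropout.

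**Plan's own figure.** 30 + 10 + 15 = 55, as SAP 3.1 states. The trial is not powered, so no power calculation applies.

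**Scheduled lung-function tests by visit**

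| Visit | Cohorts 1–2 | Cohort 3 | All | Cohort 3 share | Not scheduled, of 55 |
|---|---|---|---|---|---|
| Week 12 | 40 | 0 | 40 | 0% | 15 (27.3%) |
| Week 24 | 40 | 15 | 55 | 27.3% | 0 |
| Week 36 | 40 | 0 | 40 | 0% | 15 (27.3%) |
| Week 48 | 40 | 15 | 55 | 27.3% | 0 |

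**Missing counts under SAP 9.1.** At each of Weeks 12 and 36, up to 15 of 15 boys in the Cohort 3 column and 15/55 = 27.3% of all subjects are labelled missing by design. Over the four visits that is 30 of 4 × 55 = 220 subject-visits, or 13.6%. For functional tests the effect is confined to the Cohort 3 column, because SAP 9.6.1 summarises that cohort separately.

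**Do the windows rescue this?** A Cohort 3 Week 24 test at 168 ± 14 days falls on days 154–182, outside both windows. A Week 48 test at 336 ± 14 days falls on days 322–350, also outside both. Only an unscheduled or early-termination test could supply a value.

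**Mix effect.** Let m be the mean change from baseline in Cohorts 1–2 and m + d that in Cohort 3.

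- Weeks 12 and 36: all-subjects mean = m.
- Weeks 24 and 48: all-subjects mean = (40m + 15(m + d))/55 = m + (15/55)d = m + 0.273d.

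Mix alone therefore moves the mean by 0.273d at Week 24, back at Week 36, and again at Week 48. The documents give no d. For assumed values of 2, 5 and 10 units the shift is 0.55, 1.36 and 2.73 units. These values show scale only.

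**After the fix.** With only scheduled tests counted, by-design missing values at Weeks 12 and 36 fall from 15 of 55 to 0 of 40. Correcting the schedule alone still leaves n at 40/55/40/55. A constant mix needs either separate Cohort 3 summaries or an all-subjects column limited to Weeks 24 and 48.

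**The case against.** The strongest reply is that this is a wording inconsistency whose consequences are mostly caught elsewhere in the SAP.

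- **PCF and SNIP.** A reader might infer that they have been dropped. The documents do not support that. SAP 4.2 keeps both as secondary endpoints, 9.1 sets descriptive summaries for all endpoints by default, 9.8.8 summarises each parameter, and Section 10.0 announces no removal. What stands is that no assessment or analysis section defines them.
- **Week 1.** A reader might infer that this comparison is lost. SAP 5.1 has a Day 7 window (days 5–9) for Cohorts 2 and 3, so the data could be assigned and summarised. Section 5.4.7 still omits the visit.
- **Missing counts.** Saying that every Cohort 3 boy is counted missing goes too far. Boys off treatment before the visit are classed as discontinued, and an in-window unscheduled or termination test counts as data. Missed-visit values are not imputed (SAP 9.1.1), so the false label changes no estimate. It does give a wrong completeness count.
- **Mix.** Cohort columns are shown beside the all-subjects column, n is printed, and baselines are matched to the boys present at each visit. A careful reader would see 40 against 55. Matching baselines corrects the change within a visit but does not make successive visits comparable.
- **Reach.** Under SAP 7.0 the Week 24 interim covers Cohorts 1 and 2, and the main CSR takes only serious adverse event data from Cohort 3. Neither is affected. Section 10.0 promises later detail on cardiac MRI and on exposure relationships, but not on the items here.
- **Extension.** One could conclude from footnote c that PCF and SNIP stop at Week 48. Protocol 6.4.5 asks for both in Cohort 3 without limiting this to the main phase, so the text is ambiguous.

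**Conclusion.** The contradiction is real and should be corrected before Cohort 3 is reported. SAP 5.4.7 conflicts with SAP 4.2 and the protocol's Cohort 3 table on both visits and parameters. SAP 5.2 conflicts with that table and with most of SAP 4.3.

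The false missing count follows from SAP 9.1 combined with the true Cohort 3 schedule: up to 15 of 15 in the Cohort 3 column, and 27% of all subjects for lung function, at each of Weeks 12 and 36. It assumes planned enrolment, all 15 boys still on treatment, and no stray test in the window. The 40/55/40/55 composition comes from the same schedule plus the default all-subjects column, so rewording 5.4.7 alone would not remove it.

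The mix shift is 0.27 times the cohort difference in mean change. Any figure in lung-function units rests on an assumed difference, so the documents do not support a claim that a distortion of known size will occur. The problem is confined to the later Cohort 3 and final reports.

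**What to change.** 1. **SAP 5.4.7 and 9.8.8.** Split 5.4.7 by cohort. For Cohort 3 state baseline, Week 1 (Day 7), Weeks 24 and 48, and add PCF and SNIP. Name the parameters in 9.8.8.
2. **SAP 5.2.** Limit Weeks 12 and 36 to Cohorts 1 and 2, and align the timed function tests in SAP 4.3 with the Cohort 3 table.
3. **SAP 9.1.** Count a value as missing only if that cohort's Time and Events table schedules the assessment at that visit, as 9.7.3 already does for biopsies.
4. **All-subjects lung-function column.** Summarise Cohort 3 separately, as 9.6.1 does for efficacy, or show the all-subjects column only at Weeks 24 and 48. Either works; the first also keeps the Cohort 1–2 trend on a constant set of boys.
5. **Extension.** Reconcile footnote c of the protocol's extension table with protocol 6.4.5 on whether PCF and SNIP continue in Cohort 3.

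Items 1 to 4 cost SAP wording and table shells, with no new data. Item 5 needs a protocol clarification, or an amendment if the schedule text changes.

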5.5 Pharmacokinetics (PK)

Samples will be taken for the determination of SMT C1100, DHDI (SMT022346) and DHDIII (SMT022389) concentrations. The table below details the times when PK samples will be taken:

| Visit | Cohort | | |
|------------------|-------------------------------|-------------------------------|-----------------------------|
| | 1 | 2 | 3 |
| Day 1 | Pre-AM and 3 and 6h post-AM | Pre-AM and 3 and 6h post-AM | Pre-AM and 3 and 6h post-AM |
| Day 7 | | 4h post-AM | 4h post-AM |
| Week 4 | Pre-PM and 4 and 10 h post-PM | Pre-PM and 4 and 10 h post-PM | Pre-AM and 3 and 6h post-AM |
| Week 8 | Pre-AM and 3 and 6h post-AM | Pre-AM and 3 and 6h post-AM | |
| Week 12 | Pre-AM and 3 and 6h post-AM | Pre-AM and 3 and 6h post-AM | Pre-AM and 3 and 6h post-AM |
| Week 24 | Pre-PM and 4 and 10 h post-PM | Pre-PM and 4 and 10 h post-PM | Pre-AM and 3 and 6h post-AM |
| Week 36 | Pre-AM and 3 and 6h post-AM | Pre-AM and 3 and 6h post-AM | Pre-AM and 3 and 6h post-AM |
| Week 48 | Pre-PM and 4 and 10 h post-PM | Pre-PM and 4 and 10 h post-PM | Pre-AM and 3 and 6h post-AM |
| Extension Visits | 4h post-AM | 4h post-AM | 4h post-AM |

These concentrations will be used in a population PK (pop-PK) model through which exposure parameters (C_{max} , $C_{t_{rough}}$, and C_{av}) will be predicted for each subject. The pop-PK model may be reported separately.

Concentrations below the lower limit of quantification (BLQ) will be taken as zero for the calculation of summary statistics for the concentration data.

6.0 Analysis Sets

6.1 Screened Population

The screened population will consist of all subjects who have written informed consent/assent. This population will only be used for summarizing disposition information.

6.2 Intention-to-Treat Population

The Intent-to-Treat (ITT) population is defined as all subjects who received at least one dose of study medication.

6.3 Safety Population

The safety population is also defined as all subjects who received at least one dose of study medication.

6.4 Endpoint Populations

Separate populations will be identified for different sets of endpoints, based upon their baseline ability to be assessed for the relevant endpoints. These populations will be:

- Leg MRI/MRS Population (*Cohorts 1 and 2*)
- Cardiac MRI Population (*Cohort 3*)
- Biopsy Population
- Functional measures Population
- Blood Biomarker Population
- PK Population

All subjects in the ITT population will be included in each set if they also have at least one assessment of an endpoint in the set (which could be their baseline assessment).

Justification for exclusions from populations will be documented prior to reporting.

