4.3 Exploratory Endpoints

- Change from baseline to Week 12, 24, 36 and 48 for Cohorts 1 and 2 and from baseline to Week 24 and 48 for Cohort 3 (in the main phase of the study) measured at 6-monthly intervals for the duration of the Extension Phase in 6MWD

- Change from baseline to Week 12, 24, 36 and 48 for Cohorts 1 and 2 and from baseline to Week 24 and 48 for Cohort 3 (in the main phase of the study) measured at 6-monthly intervals for the duration of the Extension Phase in North Star Ambulatory Assessment (NSAA) global score
- Change from baseline to Week 12, 24, 36 and 48 (in the main phase of the study) measured at 6-monthly intervals for the duration of the Extension Phase in timed function tests (10 meter run/walk, time to stand)
- Change from baseline to Week 12, 24, 36 and 48 for Cohorts 1 and 2 and from baseline to Week 24 and 48 for Cohort 3 (in the main phase of the study) measured at 6-monthly intervals for the duration of the Extension Phase in paediatric outcomes data collection instrument (PODCI) scores
- Change from baseline to Week 12, 24, 36 and 48 for Cohorts 1 and 2 and from baseline to Week 24 and 48 for Cohort 3 (in the main phase of the study) measured at 6-monthly intervals for the duration of the Extension Phase in Performance of Upper Limbs (PUL)
- Change from baseline to Week 12, 24, 36 and 48 (in the main phase of the study) and measured at 6-monthly intervals for the duration of the Extension Phase of blood biomarkers, e.g., creatine kinase, matrix metallopeptidase 9 and other biomarkers
- Change from baseline to Week 48 (in the main phase of the study) and measured at 12-monthly intervals for the duration of the Extension Phase in cardiac MRI parameters (Cohort 3)
- Change from baseline in MRI leg muscle parameters measured at 6-monthly intervals for the duration of the Extension Phase (Cohorts 1 and 2)
- SMT C1100 and metabolite plasma concentrations measured at 6-monthly intervals for the duration of the Extension Phase
- Change from baseline in pulmonary function tests measured at 6-monthly intervals for the duration of the Extension Phase

It should be noted that subjects in Cohort 3 may not be able to perform all of the functional tests at baseline. Therefore the subjects included in the analyses for these tests will be test specific and based upon their baseline ability to perform the test.

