5.2.2 North Star Ambulatory Assessment

The NSAA is a functional scale specifically designed for ambulant patients affected by DMD. It is designed to test 17 activities (see [Appendix 2](#)) with scores of 0, 1 or 2 for each activity; a higher score indicating fewer limitations due to DMD. The total score will be derived as the sum of the scores from the 17 activities, and hence has the range 0-34. If the NSAA was performed but some of the activity scores are missing, then the worst score of the adjacent visits will be used to calculate the total score. For example, if the Week 24 NSAA was performed but some of the activities were missing then the worst score for the corresponding activity at Week 12 and 36 will be used.

The NSAA linearized score will also be derived ([Mayhew 2013](#)) where the NSAA scale is converted to a 0-100 scale using 16 of the activities (excludes 'lifts head').

The time to rise from the floor (time to stand) and the 10-Metre run/walk time are also collected with this assessment and are described in sections below as independent endpoints.

If the subject is unable to perform the assessment the reason will be recorded. If the reason given for not performing the assessment is related to the subject's medical condition (i.e. informative) the activity score will be taken as zero, otherwise it will be taken as missing.

Changes from baseline in the total score and the linearized score will be calculated.

The following velocities of change (change per month) will also be calculated for the total and linearized scores:

- Baseline to Week 12
- Week 12 to Week 24
- Week 24 to Week 36
- Week 36 to Week 48

And

- Baseline to Week 24
- Week 24 to Week 48

... and so forth when reporting the extension phase data

Loss of ambulation will be determined by a score of 0 with the 'walk' activity in the NSAA. To ensure the subject's disease has truly reached this level, subsequent visits will also need to have a score of 0.

The number of functions (0, 1, 2...) a subject has lost ("unable"), compared to baseline, will also be determined at each visit. Again, to ensure, that the subject's disease has truly reached this level subsequent visits will also need to have a score of 0.

5.2.3 10-Metre Run/Walk

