The 10-metre run/walk should be performed once at each visit and only repeated if the evaluator deems it to be spurious. The protocol incorrectly states that the test should be repeated after a 10 minute rest and both times recorded on the eCRF. The error was documented in a file note (SMTC11005-006 Dated: 05Oct2017). As a consequence, the majority of patients only have one test performed at a visit however if there is a repeat test then the shortest time (duration) of the completed tests will be used in analyses. If the subject is unable to perform the assessment or is unable to complete it, the reason will be recorded. For an assessment not completed the distance and duration of time walked will also be recorded.

If the reason given for not performing at any assessment or not completing any assessment is related to the subject's medical condition (i.e. informative) the time will be taken as the worst score recorded (over all subjects and assessments) whilst on treatment or the derived time adjusted for the distance recorded respectively.

The derived time adjusted for the distance = (10/distance in metres) x time recorded.

Changes from baseline will be calculated.

The following velocities of change (change per month) will also be calculated:

- Baseline to Week 12
- Week 12 to Week 24
- Week 24 to Week 36
- Week 36 to Week 48

And

- Baseline to Week 24
- Week 24 to Week 48

... and so forth when reporting the extension phase data

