9.6 Efficacy Analyses

9.6.1 General

All analyses will be performed on the functional measures population.

Tabulations will be over all Cohorts 1 and 2 subjects and will not provide separate information for the two cohorts. Cohort 3 data will be summarized separately. In addition to the standard set of descriptive statistics summaries will also tabulate the number of subjects where their value has been imputed (see [Section 9.1](#)). The 95% confidence interval will also be included for the mean changes from baseline.

Box and whisker plots will display the Baseline, Weeks 12, 24, 36 and Week 48 data.

Mean changes from baseline, with associated 95% confidence intervals, will be plotted against visit. As visits in the extension phase will be included the plot will also include the n contributing to the visit.

The velocity of change per month will be assessed for specific endpoints. Velocities will be estimated using mixed effect models of the absolute values, including baseline. The model will include visit as a fixed effect term and subject as a random effect term. The following will be estimated along with 95% confidence intervals:

Velocity (12-B): (Week 12 – Baseline)/3

Velocity (24-12): (Week 24 – Week 12)/3

Velocity (36-24): (Week 36 – Week 24)/3

Velocity (48-36): (Week 48 – Week 36)/3

And

Velocity (24-B): (Week 24 – Baseline)/6

Velocity (48-24): (Week 48 – Week 24)/6

...

The following differences between velocities will also be estimated along with 95% confidence intervals:

Velocity (24-12) – Velocity (12-B)

Velocity (36-24) – Velocity (12-B)

Velocity (48-36) – Velocity (12-B)

And

Velocity (48-24) – Velocity (24-B)

...

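### SAP 6.4 and 9.6.1 do not implement the test-specific rule for Cohort 3: inability imputation has no post-baseline limit, and loss of ambulation has no baseline-walking condition

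*SAP*

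**What the plan says.** **Who is analysed.** SAP 4.3 warns that "subjects in Cohort 3 may not be able to perform all of the functional tests at baseline" and therefore that "the subjects included in the analyses for these tests will be test specific and based upon their baseline ability to perform the test". Protocol 3.3 says the same. SAP 6.4 opens in that spirit: "Separate populations will be identified for different sets of endpoints, based upon their baseline ability to be assessed for the relevant endpoints". Its operative sentence, however, admits treated subjects who "will be included in each set if they also have at least one assessment of an endpoint in the set", and adds that the assessment may be the baseline one. There is one functional set, and SAP 9.6.1 states "All analyses will be performed on the functional measures population". That section covers 6MWD, NSAA, 10-metre run/walk, time to stand, PODCI and PUL.

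**Inability.** SAP 5.2 lists baseline among the efficacy assessments and treats physical inability as informative, without a time limit. The rules by test are:

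- NSAA (5.2.2): if the reason is medical, "the activity score will be taken as zero, otherwise it will be taken as missing".
- 10-metre run/walk (5.2.3): the rule begins "If the reason given for not performing at any assessment or not completing any assessment is related to the subject's medical condition" and, for a test not performed, substitutes the worst on-treatment time over all subjects.
- Time to stand (5.2.4): the worst time recorded over all subjects.
- PUL (5.2.6): zero.
- 6MWD (5.2.1): zero, but the rule follows a sentence about inability after Day 1.
- PODCI (5.2.5): no imputation.

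**Loss of ambulation.** SAP 5.2.2: "Loss of ambulation will be determined by a score of 0 with the" walk item, repeated at subsequent visits. Nothing requires the boy to have walked at baseline. The next rule in that section, on the number of functions lost, is relative to baseline. SAP 9.6.3 reports loss of ambulation as number and percentage by visit, and SAP 9.1 sets the default denominator as the study population.

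**The concern.** Boys unable to do some tests are foreseen only in Cohort 3. The 300-metre walking criterion does not apply to that cohort (Protocol 5.2.1.1), and the Protocol Summary describes the population of interest as older and less ambulant. A boy already at the floor of a scale cannot decline on it. If he stays in the table with a fixed value at each visit, the mean change moves towards no deterioration and its confidence interval narrows. The loss-of-ambulation table errs in the other direction.

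Cohort 3 has no concurrent control. Protocol 1.2 foresees comparing its boys with natural-history data and using the cohort to help design a pivotal study. SAP 7.0 plans analyses once the cohort completes Week 48 and before submission. A diluted decline, or an inflated loss of ambulation, would carry into those uses.

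**Working it through.** The documents give no power, effect size or standard deviation for these endpoints, so there is no planned figure to reproduce.

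**Inputs.** Cohort 3 size n = 15 (SAP 3.1, approximate). k = boys unable to do a given test at baseline and at every later visit; it is not given, it may differ by test, and it is varied here. e = boys who truly lose ambulation during the study; also assumed.

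**Step 1: one boy through the rules.** A boy who cannot walk has a completed PODCI, so he enters the set.

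- *Baseline imputed.* NSAA change = 0 − 0 = 0. His 10-metre and time-to-stand changes are the worst time minus the same worst time, which is 0.
- *Baseline left missing.* SAP 5.1 defines baseline as the last non-missing pre-dose assessment. If an unperformed test counts as missing, he has no change score. He still receives the imputed value at Weeks 24 and 48, so his Week 24–48 velocity is exactly 0. This holds for 6MWD too, because its zero rule applies after Day 1.
- *PUL.* A zero change arises only if he cannot do the PUL. Being non-ambulant does not by itself produce one.

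**Step 2: dilution.** Mean over all 15 = mean among able boys × (15 − k)/15, so the shrinkage is k/15. It applies to the change from baseline under the first reading and to the descriptive Week 24–48 velocity under both, assuming all 15 have values.

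For illustration, assume an NSAA change of −4 (SD 4) among the a = 15 − k able boys. These two figures are not from the documents. With M the mean over all 15, the pooled sum of squares is (a − 1)·4² + a(−4 − M)² + k·M², and the SD is the square root of that sum over 14. For k = 5, M = −2.67, the sum is 144 + 17.8 + 35.6 = 197.3, and the SD is 3.75.

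| k | Shrinkage | Able boys only, mean (95% CI) | All 15, mean (95% CI) |
|---|---|---|---|
| 1 | 6.7% | −4.00 (−6.31 to −1.69) | −3.73 (−5.94 to −1.52) |
| 3 | 20.0% | −4.00 (−6.54 to −1.46) | −3.20 (−5.37 to −1.03) |
| 5 | 33.3% | −4.00 (−6.86 to −1.14) | −2.67 (−4.75 to −0.59) |
| 8 | 53.3% | −4.00 (−7.70 to −0.30) | −1.87 (−3.71 to −0.02) |

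**Step 3: loss of ambulation.** Here k counts boys with a walk score of 0 from entry onwards. The rule as written gives (k + e)/15; among boys at risk the proportion is e/(15 − k).

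| k | As written, e = 0 | At risk, e = 0 | As written, e = 1 | At risk, e = 1 |
|---|---|---|---|---|
| 1 | 6.7% | 0% | 13.3% | 7.1% |
| 3 | 20.0% | 0% | 26.7% | 8.3% |
| 5 | 33.3% | 0% | 40.0% | 10.0% |
| 8 | 53.3% | 0% | 60.0% | 14.3% |

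This step does not depend on how baseline is handled: a walk score of 0 at Weeks 24 and 48 is enough.

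**The case against.** A reader might infer that the SAP has decided to impute baseline values for unable boys. It has not said so. The rules in 5.2.2–5.2.4 and 5.2.6 merely lack a time limit, and the baseline definition in 5.1 allows the other reading, under which the zero changes from baseline disappear. That part of the point is therefore conditional.

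The test-specific intention is also still in force in SAP 4.3 and is echoed at the start of 6.4. One could treat 6.4 as a broad set from which each table is then drawn. That is possible, but neither 6.4 nor 9.6.1 provides a per-test set from which to program, and 9.6.1 names the broad set for every analysis.

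Nor do the documents show that many Cohort 3 boys are non-ambulant. SAP 3.0 describes ambulatory patients, the criterion of ongoing difficulty with walking applies to Cohort 3, and a boy may miss Cohorts 1 and 2 on age alone. With k = 0 there is no effect.

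The reach is limited as well. The endpoints are exploratory, Cohort 3 is never combined with the others for efficacy (SAP 10.0), and the main study report takes only its serious adverse events (SAP 7.0). Imputed values are counted in each table (SAP 9.1), and shift tables for each NSAA activity (SAP 9.6.3) would reveal a boy at 0 throughout. These outputs let a careful reader detect the problem. They do not remove such boys from the mean, the interval or the loss-of-ambulation percentage.

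**Conclusion.** The point holds in three parts of different strength.

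1. The analysis set in SAP 6.4 and 9.6.1 does not implement the rule in SAP 4.3 and Protocol 3.3. This is an unreconciled conflict.
2. The inability rules for four tests leave baseline open. On the literal reading, the Cohort 3 mean change shrinks by k/15. On the other reading, the Week 24–48 velocity still receives exact zeros for NSAA, 10-metre run/walk, time to stand and 6MWD.
3. The loss-of-ambulation definition is wrong as written for a boy non-ambulant at entry, whichever reading is taken, and its default denominator includes boys not at risk.

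The size depends wholly on k, which the documents do not give: 7% for k = 1, 20% for k = 3, 33% for k = 5, 53% for k = 8, with 15 boys. The NSAA figures are illustrations. It would be too strong to conclude that the trial's main results are biased. Cohorts 1 and 2 must walk 300 metres at entry and are not affected, and no leg MRI, biopsy or pulmonary endpoint is involved. The matter is worth correcting because the rules as written can give a wrong Cohort 3 table and the correction is simple.

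**What to change.** Amend the SAP as follows:

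- **6.4 and 9.6.1:** replace the single functional set with one set per test, consisting of boys who actually performed that test at baseline.
- **5.2.2, 5.2.3, 5.2.4 and 5.2.6:** state that imputation for an informative reason applies only after Day 1, in line with 5.2.1.
- **5.2.2 and 9.6.3:** limit both numerator and denominator of loss of ambulation to boys with a baseline walk score of 1 or 2.

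No new data or protocol amendment is needed, and SAP 10.0 already expects a later version for other Cohort 3 details. The cost is a smaller n, and so wider intervals, for some Cohort 3 tests. The number of boys excluded from each test should be shown beside the table.
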